8.5.2 Interim Analysis

An interim analysis will be completed after 14 subjects have completed the intermediate assessment for CBR at Visit 9. At this time, the safety and preliminary efficacy of the study dose will be assessed and if, deemed safe and appropriate, enrollment may continue as needed to achieve up to 24 evaluable subjects to increase the degree of precision of the standard error.

8.5.3 Safety Analysis

All subjects entered into the study will have detailed information collected on AEs for the overall study safety analysis. Treatment emergent AEs are defined as AEs with a start date or that increase in severity on or after the first study drug dose through Visit 15 of the Follow Up Phase of the study.

8.6 Subject Population(s) for Analysis

Any subject enrolled into the study that receives at least one dose of investigational product will be included for all analyses for each Visit they complete.

9 Safety and Adverse Events

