3.2 Study Endpoints

3.2.1 Primary Study Endpoints

The primary endpoint of this study will be the proportion of patients achieving a positive CBR response (**Section 7.6**, **Efficacy Evaluations**) at 12 ± 1 month. Assessments at 12 ± 1 month will be compared to those obtained at the Baseline Visit.

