6.2.11 End of Treatment Visit (Visit 15)

Subjects will complete the treatment at 12 ± 1 month following administration of loading dose and return to the study site for their final, End of Treatment Visit (Visit 15). Participants who choose to discontinue or who are withdrawn from the study will complete an Early Termination Visit (**Section 6.7**). It is highly encouraged that this visit occurs at the study site, but at the physician's discretion, this visit may occur remotely and subject may visit their local medical provider or facility (e.g. Quest Diagnostics). The below procedures will be conducted as standard of care:

- Physical exam including performance score (if visit occurs on site)
- Vital signs (if visit occurs on site)
- Radiological imaging (PET/CT or CT)
- Standard of Care Laboratory Tests (Appendix 15.4)
- Lipid panel
- Review of medication changes and updates

The below non-standard of care procedures will be conducted as part of this study during Visit 15:

- Research blood draw
- Pregnancy testing for females of childbearing potential (may be self-administered by subjects if visit is conducted remotely)
- Sirolimus Trough
- Assess possible AEs
- Return of any non-consumed sirolimus
- Sirolimus pill count (if visit occurs on site)
- Final assessment of primary objective
- Recording of medical history data, medication changes, AEs, and Laboratory Test, as available, (Appendix 15.4) from medical records into eCRF

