6.7 Early Termination Visit

Subjects who discontinue or are withdrawn early from the study will return to the study site for a final Early Termination Visit. Unless conducted as standard of care, the below standard of care procedures will be performed:

- Physical exam including performance score
- Vital signs

- Standard of Care Laboratory Tests (Appendix 15.4)
- Review of medication changes and updates

The below non-standard of care procedures will be conducted as part of this study during the Early Termination Visit:

- Research blood draw
- Assess possible AEs
- Return of any non-consumed sirolimus
- Sirolimus pill count
- Recording of medical history data, medication changes, AEs, and Laboratory Test, as available, (Appendix 15.4) from medical records into eCRF

7 Study Evaluations and Measurements

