7.6 Efficacy Evaluations

The below measures will be used to assess the efficacy of the study intervention and determine if the subject meets criteria for a CBR. All comparisons are against those obtained during the Baseline Visit:

Positive response: Relative to baseline, improvement in at least one of the below criterion without worsening of any single criterion other than hemoglobin on two consecutive study visits.

Negative response: Relative to baseline, worsening of any single criterion other than hemoglobin on two consecutive site visits or failure to achieve improvement for any criterion.

	Hemoglobin	Fatigue	Anorexia	Fever and night sweats	Weight	Lymph node size
Improvement	≥2 g/dL increase without transfusions	≥1 grade decrease by NCI CTCAE version 4.0, May, 2009	≥1 grade decrease by NCI CTCAE version 4.0, May, 2009	≥2°C decrease in fever or return to normal body temperature (37°C) or improvement in night sweats, as assessed by licensed site investigator	≥5% increase not due to increase in new or existing edema	≥25% decrease bi-dimensionally in size of largest lymph node, as measured using Cheson criteria (Appendix 15.2)
Worsening		≥2 grade increase by NCI CTCAE version 4.0, May, 2009	≥2 grade increase by NCI CTCAE version 4.0, May, 2009	≥2°C increase in fever or worsening in night sweats, as assessed by licensed site investigator	≥5% decrease (weight loss not due to decreased edema)	≥25% increase bidimensionally in size of largest lymph node, as measured using Cheson criteria (Appendix 15.2)

The below table provides the CHAP score, which will be used to assess the efficacy of the study intervention. All comparisons are against those obtained during the Baseline Visit:

Score:	0	1	2	3	4
CRP (mg/dL)	<1	≥1, <5	≥5, <10	≥10, <20	≥20
Hemoglobin (g/dL)	≥12	<12, ≥10	<10,≥8	<8	Transfusion dependent
Albumin (g/dL)	≥3	<3,≥2.5	<2.5, ≥2	<2, ≥1.5	<1.5
Performance Score (ECOG)	0	1	2	3	4

The below table provides the modified Cheson response criteria, which will be used to assess the efficacy of the study intervention. Unless otherwise specified, all comparisons are against those obtained during the Baseline Visit:

Complete Response (CR)	All index lesion(s) must have regressed to normal size (≤1.0 cm in		
	their greatest transverse diameter. No new sites of		
	lymphadenopathy >1.5 cm in longest dimension.		
Partial Response (PR)	≥50% decrease in sum of the products of the greatest diameters		

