9.7.2 Data Safety Monitoring Board

An independent DSMB will be established to assure the safety of subjects in this trial. The DSMB will review the study for safety and overall study conduct. At the end of the study, they may adjudicate final outcome based on the clinical information. The membership of the DSMB as well as the responsibilities and procedures used to carry out these responsibilities are described separately in the DSMB charter.

10 Study Administration, Data Handling and Record Keeping

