10.2 Data Collection and Management

Study data, collected as part of the trial, as standard of care treatment during the trial period, and historic medical and treatment information will be entered into the eCRF. The eCRF is the primary data collection instrument for the study. All data requested on the eCRF must be recorded. All missing data must be explained. If a space on the eCRF is left blank because the procedure was not done or the question was not asked, write "N/D". If the item is not applicable to the individual case, write "N/A".

A shared database with common data definitions will be created using REDCap, and housed on a secure server at the University of Pennsylvania. REDCap is a secure, web-based application with the capacity for direct export to Excel and common statistical packages (SPSS, SAS, Strata,

R). REDCap has eCRFs, real-time data entry validation, audit trails, user authentication, data logging and encryption. It is HIPAA compliant with mechanisms in place to ensure confidentiality.

To ensure confidentiality of the data, subjects GUIDs will be used for identification in REDCap; personal identifiers (e.g. name, social security number, medical record number, etc.) will not be entered into the eCRF. Qualified study staff will have access to all study data collected in the eCRF.

Specific forms will be used for each component of the subject's progress. The forms and data dictionary will be available online for all individuals who perform data entry. Research personnel, trained on data definitions, will enter data via web-based data forms after abstraction from the primary medical record and source documents. Logical data checks will be used to assess data quality for mis-entry. Suspect data entries will be flagged for re-review and confirmation by the investigative team at each site. When data are complete and all suspect entries addressed for a time period, the database will be "locked" for analysis. Analysis will use only this final locked version. De-identified data will be stored indefinitely.

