15.3 Study calendar

Study Phase	Screening	Baseline Phase	Intervention Phase							Early	Follow-up Phase							
Study Visit Number	Screening	1	2	3	4	5	6	7	8	9	10	11	12	13	14	15	Terminati	16
Study Days**	-28 to 0**	-7 to 0**	5 ± 2 days	14 ± 5 days	1 month ± 1 week	2 months ± 2 weeks	3 months ± 2 weeks	4 months ± 2 weeks	5 months ± 2 weeks	6 months ± 2 weeks	7 months ± 2 weeks	8 months ± 2 weeks		10 months ± 2 weeks			on Visit	12 ± 2 weeks following the End of Study Visit
Diagnostic Laboratory Tests*	Х																	
Physical Exam*		X			X***		X***			X***			X***			X***	X***	
Vital Signs*	x	x			X***		X***			X***			X***			X***	X***	
Radiological Imaging*	X						X			X			X			x		
Lipid Panel	x	X			X		X			x			X			x		
Review of concomitant medications*	X	X																
Confirmation subject meets enrollment criteria	x	x																
Informed Consent	x																	
Pregnancy Test (urine)	X				X		X			X			X			x	X	
GUID assigned		X																
Research blood draw		X	x	х	X	х	X	X	X	X	x	X	X	x	х	х	X	
Fecal sample collection (optional)		X		X						X								
Recording of Demographic information in to eCRF	x																	
Recording of medical history data, medications, possible AEs and Laboratory Test, as available, from medical records into eCRF		x	x	x	х	x	x	x	x	x	x	x	x	x	x	x	x	
Completion of Patient Evaluation Form and confirmation subject is eligible by Lead PI	x	x																
Dispensing of sirolimus loading dose**		x																
Dispensing of sirolimus daily dose		X			X		X			X			X					
Assess possible AEs, study drug compliance, and medication changes			x	x	x	x	x	x	x	x	x	x	x	x	x	x	x	х
Sirolimus Trough			x	X	X		X			X			X			х	x	
Standard of Care Laboratory Test*					X		X			X			X			X	X	
Return of any non-consumed sirolimus					X		X			x			X			x	x	
Sirolimus pill count***					X		X			X			X			X	X	
Intermediate assessment of primary objective							x			x				x		^	~	
Final assessment of primary objective																x		
Follow Up telephone questionnaire																		X

^{*}Standard of Care for iMCD

^{**}Indicated times are following loading dose

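### Section 8.6 counts dosed subjects only at visits they complete, so early leavers probably fall out of the Month-12 CBR denominator and the primary rate is likely biased upward

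*Combined protocol and SAP*

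**What the plan says.** Section 3.2.1 defines the primary endpoint as "the proportion of patients achieving a positive CBR response" at 12 ± 1 month compared with baseline, and Section 8.1 repeats it. Neither says which patients form the denominator. The only population rule is in Section 8.6, where any enrolled subject given at least one dose "will be included for all analyses for each Visit they complete".

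The Month-12 assessment belongs to Visit 15. The study calendar (Appendix 15.3) has a row for "Final assessment of primary objective" that is marked once, at the end of treatment. Early leavers take a different route. Section 6.2.11 states: "Participants who choose to discontinue or who are withdrawn from the study will complete an Early Termination Visit". Section 6.7 lists that visit's content: physical examination, vital signs, laboratory tests, a research blood draw, adverse events and drug return. Imaging and assessment of the primary objective are not on the list, and the calendar agrees.

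Section 6.6 allows withdrawn subjects to be replaced. Section 8.4 explains the gap between up to 40 enrolled and 24 evaluable subjects partly by dropouts who are replaced. *Evaluable* is not defined anywhere.

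**The concern.** Read together, these sections mean that a subject who stops early completes no Month-12 visit, contributes nothing to the Month-12 analysis, and may have their place taken by someone else. The reported rate then applies to subjects still attending at one year.

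Leaving is unlikely to be independent of outcome. Section 6.4 allows removal for progression or a serious adverse event. Section 6.6 lists progressive disease, intolerable adverse events and use of other systemic iMCD therapy. Some listed reasons, such as pregnancy and withdrawn consent, need have nothing to do with failure.

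In a single-arm trial the response rate and its 95% confidence interval (Section 8.5.1) are the main result. Section 8 says that enrolling beyond 14 subjects serves to improve that estimate, and it sets 20% as the minimal acceptable activity. A result near that level could read as at or above 20% among completers and below 20% among all treated subjects.

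**Working it through.** **Does any other section put leavers back in the denominator?** Three candidates were checked.

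- Section 7.6 calls a response negative on "failure to achieve improvement for any criterion". This is a comparison of measurements with baseline and does not classify a subject who was never measured at Month 12.
- Section 10.2 says "All missing data must be explained". This is a rule for completing the eCRF, not an analysis rule.
- Section 9.7.2 says of the DSMB that "they may adjudicate final outcome based on the clinical information". This is optional and gives no rule for missing outcomes.

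The secondary endpoint on remaining on study drug (Section 8.2) will show how many left but does not change the CBR rate. No section imputes, carries values forward, counts leavers as non-responders or plans a sensitivity analysis.

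**The plan's own figure.** The sample size of 14 follows from the zero-response interim rule: 0.8^14 = 0.044, below 0.05, while 0.8^13 = 0.055. The present point does not depend on it. The plan gives no dropout rate, so the number of leavers is assumed below.

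**Formula.** Let x be Month-12 responders, c completers and d dosed leavers, with no leaver counted as a responder.

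- Completer rate = x / c
- All-dosed rate = x / (c + d)
- Ratio of the two = (c + d) / c

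Intervals are exact (Clopper-Pearson) 95%. Five is the smallest count that reaches 20% of 24 (4/24 = 16.7%; 5/24 = 20.8%), so x = 5 shows the case nearest that level and x = 8 a higher response.

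| x | c | d | Completer rate (95% CI) | All-dosed rate (95% CI) |
|---|---|---|---|---|
| 5 | 24 | 1, replaced | 20.8% (7.1–42.2) | 5/25 = 20.0% (6.8–40.7) |
| 5 | 24 | 2, replaced | 20.8% (7.1–42.2) | 5/26 = 19.2% (6.6–39.4) |
| 5 | 24 | 4, replaced | 20.8% (7.1–42.2) | 5/28 = 17.9% (6.1–36.9) |
| 5 | 24 | 8, replaced | 20.8% (7.1–42.2) | 5/32 = 15.6% (5.3–32.8) |
| 8 | 24 | 4, replaced | 33.3% (15.6–55.3) | 8/28 = 28.6% (13.2–48.7) |
| 8 | 24 | 8, replaced | 33.3% (15.6–55.3) | 8/32 = 25.0% (11.5–43.4) |
| 5 | 20 | 4, not replaced | 25.0% (8.7–49.1) | 5/24 = 20.8% (7.1–42.2) |

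The last row shows that replacement is not needed for the effect: the ratio is 24/20 = 1.20.

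**Direction.** If r of the d leavers would have responded at Month 12, the all-dosed rate is (x + r) / (c + d). It exceeds the completer rate when r/d is greater than x/c. Starting from 5/24 = 20.8%:

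- d = 4, r = 1: 6/28 = 21.4%, so the sign reverses.
- d = 8, r = 1: 6/32 = 18.8%, still lower.
- d = 8, r = 2: 7/32 = 21.9%, so the sign reverses.

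The completer rate is therefore too high exactly when leavers would respond less often than completers.

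**The case against.** The strongest reply has four parts.

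**No decision turns on the shift.** The 20% level is tied to the interim zero-response rule, the stated null is 0%, and every interval above excludes 0% under either denominator. Moving from 20.8% to 17.9% is about 3 points inside an interval 35 points wide, and the 5-responder example sits at the edge of 20%. This is correct, and the point is not put as a change of decision. But the trial's main product is an estimate, and a wide interval around a completer rate still describes the wrong population.

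**The wording is ambiguous.** The opening of Section 8.6 could be taken to keep every dosed subject, and a sponsor could score leavers as negative under Section 7.6. That is possible. But the qualifier about completed visits and the replacement language in Section 8.4 favour the completer reading. Even on the kinder view, two analysts could report different primary results from the same data.

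**The direction is fragile.** Several withdrawal reasons do not indicate lack of efficacy, and one would-be responder among four leavers reverses the sign. This stands, and it is why the bias is called likely and not certain. Counting leavers as not positive is also a choice of estimand, though a common one.

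**There is partial mitigation.** CBR at 3, 6 and 9 months is reported, so leavers contribute until they go. The Early Termination Visit also collects data on some CBR components, and one improved criterion can suffice. None of this enters the Month-12 rate under the present text.

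**Conclusion.** The concern holds. Followed as written, Section 8.6 most naturally gives a Month-12 CBR rate among completers, and no other section restores early leavers to the denominator. Relative to counting leavers as not positive, the rate is inflated by dosed/completers: 28/24 = 1.17 with 4 replaced leavers, 32/24 = 1.33 with 8, and 1.20 if 4 of 24 leave unreplaced. For 5 responders among 24 completers, 2 or more non-responding leavers take the all-dosed rate below 20%. For 8 responders the rate stays above 20% in both cases shown.

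These sizes rest on assumed dropout and on leavers not responding; the documents fix neither. Upward bias is the likely direction given the listed reasons for leaving, but it can vanish or reverse. The interim rule is not part of this finding.

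**What to change.** Add to Section 8.6, before the data are analysed:

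1. The primary Month-12 CBR proportion uses every subject who received at least one dose, including any later replaced.
2. A subject who left, started other iMCD therapy, or has no Month-12 CBR assessment counts as not positive.
3. The completer rate is a sensitivity analysis, shown with a table of reasons for leaving. Subjects still on drug but lacking a Month-12 assessment have their own row.
4. The proportion remaining on study drug also uses all dosed subjects.
5. *Evaluable* is defined in one sentence (for example, dosed with a Visit 15 CBR assessment), and the text states that it governs the enrolment target in Section 8.4 and not the denominator.

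Because Visit 15 may be remote, item 2 should also say which of the six criteria must be available for a Month-12 assessment to count as made. Leave the interim rule as it is.

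The cost is wording in Section 8.6, with Sections 4.5, 8.2 and 8.4 checked for consistent terms. No extra patients or procedures are needed. The headline rate may be lower, and some subjects who leave for unrelated reasons or miss the assessment are scored as not positive. The sensitivity analysis and the table of reasons make that visible.

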9.1 Definitions

9.1.1 Adverse Event

An adverse event (AE) is any symptom, sign, illness or experience that develops or worsens in severity during the course of the study. Intercurrent illnesses or injuries should be regarded as AEs. Abnormal results of diagnostic procedures are considered to be AEs if the abnormality:

- results in study withdrawal
- is associated with a serious AE
- is associated with clinical signs or symptoms
- leads to additional treatment or to further diagnostic tests
- is considered by the licensed site investigator to be of clinical significance

9.1.2 Serious Adverse Event

AEs are classified as serious or non-serious. A serious adverse event is any AE that is:

- fatal
- life-threatening
- requires or prolongs hospital stay
- results in persistent or significant disability or incapacity
- a congenital anomaly or birth defect
- an important medical event

Important medical events are those that may not be immediately life threatening, but are clearly of major clinical significance. They may jeopardize the subject, and may require intervention to prevent one of the other serious outcomes noted above. For example, drug overdose or abuse, a seizure that did not result in in-patient hospitalization, or intensive treatment of bronchospasm in an emergency department would typically be considered serious.

All AEs that do not meet any of the criteria for serious should be regarded as non-serious AEs.

9.2 Recording of Adverse Events

At each contact with the subject, study staff will seek information on AEs by specific questioning and, as appropriate, by examination. Subjects will be monitored for all previously reported AEs associated with sirolimus treatment and possible new AEs, as well as Grade 2 or higher allergic reaction/hypersensitivity attributed to sirolimus, as judged by the site investigator. AEs will be defined by the NCI CTCAE version 5.0, November 2017. All AEs will be recorded in the source document, and also in the appropriate AE module of the eCRF. All clearly related signs, symptoms, and abnormal diagnostic procedures' results should be recorded in the source document, though should be grouped under one diagnosis.

AEs occurring during the study period (from the time of enrollment through Visit 15) will be recorded. The clinical course of each event should be followed by the licensed site investigator until resolution, stabilization, or until it has been determined that the study treatment or participation is not the cause.

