1.2.2.1 Human Pharmacokinetics

The pharmacokinetics of sirolimus have been studied in healthy subjects, pediatric dialysis patients, hepatically-impaired adult patients, and adult renal transplant patients. 36,37 Oral doses are rapidly, though variably, absorbed. Mean time-to-peak concentrations range from 1 hour in healthy subjects to 2 hours in renal transplant recipients. Half-life is upwards of $2\frac{1}{2}$ days. Patients who ingested the drug after a high fat breakfast did have delayed C_{max} and it is recommended to take sirolimus consistently with or without food.

The plasma protein binding of sirolimus is approximately 92% mainly to albumin, alpha-1-acid glycoprotein and lipoproteins, and has a high level of association with erythrocytes. The systemic availability of sirolimus was estimated to be approximately 14%. Sirolimus is extensively metabolized by O-demethylation and/or hydroxylation to at least seven major metabolites. The parent drug contributes to more than 90% of the immunosuppressive activity. The main route of elimination is through the feces (91%). The mean half-life increased from 79 ± 12 hours in subjects with normal hepatic function to 113 ± 41 hours in patients with impaired hepatic function. Males have a 12% lower clearance of sirolimus than females after oral solution administration. In some studies, the immunosuppressive effect of sirolimus lasts up to 6 months after discontinuation of therapy. No differences were demonstrated between black and non-blacks. Sirolimus is a substrate for both cytochrome P450 IIIA4 (CYP3A4) and P-glycoprotein (P-gp). Sirolimus is extensively metabolized by the CYP3A4 isozyme in the intestinal wall and liver and undergoes counter-transport from enterocytes of the small intestine into the gut lumen by the P-gp drug efflux pump. Sirolimus is potentially recycled between enterocytes and the gut lumen to allow continued metabolism by CYP3A4. Therefore, absorption and subsequent elimination of systemically absorbed sirolimus may be influenced by drugs that affect these proteins. Drugs that stimulate or inhibit p-450 enzymes will alter clearance of sirolimus and close attention to potential drug interactions is crucial. Care should be exercised when drugs or other substances that are metabolized by CYP3A4 are administered concomitantly with sirolimus. Grapefruit juice reduces CYP3A4-mediated metabolism of sirolimus; subjects will be advised to avoid ingesting grapefruit.

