3.1.3 Follow Up Phase

Subjects will be contacted via telephone 12 ± 2 weeks following the End of Treatment Visit or Early Termination Visit to document changes in health, medications and to monitor for pregnancy.

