6.3 Follow Up Phase of the Study

6.3.1 Visit 16

The subject will be contacted by phone 12 weeks \pm 2 weeks after the End of Treatment Visit or Early Termination Visit and asked questions regarding their health status, if they have become pregnant (if applicable), and if they have continued on drug off-study.

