12.1 Risks

The risk to patients of exposure to the treatment intervention, sirolimus, as related to AEs is relatively low. Sirolimus is an FDA-approved therapy with an established safety profile. Although uncommon, AEs are possible and will be monitored by study staff and licensed site investigators. The most common (≥20%) adverse reactions reported for sirolimus 2 mg/day at a higher incidence than reported for placebo include:

- peripheral edema
- hyperlipidemia, hypercholesterolemia, hypertriglyceridemia
- increased creatinine
- constipation
- hypertension
- abdominal pain / diarrhea
- headache
- arthralgia

Other less common serious complications include:

- angioedema
- leucopenia
- thrombocytosis / thrombocytopenia
- fluid accumulation

- impaired wound healing
- proteinuria
- interstitial lung disease/non-infectious pneumonitis
- calcineurin inhibitor-induced hemolytic uremic syndrome/thrombotic thrombocytopenic purpura/thrombotic microangiopathy

The below table summarizes the known adverse events (AEs) categorized based on timing and frequency:

Known Adverse Events (AEs)									
	Common	Occasional	Rare						
	21-100 out of every 100	5-20 out of every 100	<5 out of every 100						
Immediate: 1-2 days of receiving drug	Nausea, vomiting, oral ulcers	Rash	Allergic reaction (may be life threatening)						
Prompt: 2-3 weeks on drug	Increased cholesterol, increased blood pressure, decreased kidney function, diarrhea	Infections, swelling, weight gain, muscle/joint pain, tremor, acne, rash, abdominal pain, mucositis, headache	Decreased red and white blood cells generated in bone marrow, decreased liver function						
Delayed: Any time later during therapy, excluding the above conditions	Acne		Malignancy resulting from this treatment, destruction of red blood cells and decreased kidney function, interstitial lung disease, hemolytic uremic syndrome/thrombotic thrombocytopenic purpura*						
Late: Any time after completion of treatment			Interstitial lung disease						
Sirolimus was embryo/feto toxic in rats at dosages of 0.1 mg/kg and above (approximately 0.2 to 0.5 is the clinical doses adjusted for body surface area). Embryo/feto toxicity was manifested as mortality and reduced fetal weights (with associated delays in skeletal ossification). Sirolimus is excreted in trace amounts in milk of lactating rats. It is not known whether sirolimus is excreted in human milk.									

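### AE recording and the treatment-emergent window close at the End of Treatment Visit, so AEs starting or worsening in the 12-week follow-up fall outside the safety analysis

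*Combined protocol and SAP*

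**What the plan says.** Two sections set the AE window:

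- Section 9.2: "AEs occurring during the study period (from the time of enrollment through Visit 15) will be recorded".
- Section 8.5.3 counts an AE as treatment-emergent if it starts or becomes more severe "on or after the first study drug dose through Visit 15 of the Follow Up Phase of the study".

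Other sections describe the visits differently:

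- Section 6.2.11, under the Intervention Phase, makes Visit 15 the End of Treatment Visit at 12 ± 1 month.
- Section 3.1.3, on the Follow Up Phase: "Subjects will be contacted via telephone 12 ± 2 weeks following the End of Treatment Visit or Early Termination Visit". Section 6.3 lists one visit in that phase, Visit 16.
- Section 6.3.1: at that call subjects are "asked questions regarding their health status", and about pregnancy and whether they have stayed on sirolimus off study. Recording of AEs is not listed.
- Section 15.3: the row "Assess possible AEs, study drug compliance, and medication changes" is marked at Visits 2 to 15, Early Termination and Visit 16. The row for entering medical history, medications and possible AEs into the eCRF is marked at Visits 1 to 15 and Early Termination, and is blank at Visit 16.
- Section 9.2 also has staff ask about AEs at every contact, and the Visit 16 call is a contact.

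**The concern.** The protocol itself gives reasons to expect drug-related events after dosing stops. Section 1.2.2.1 reports that, in some studies, "the immunosuppressive effect of sirolimus lasts up to 6 months after discontinuation of therapy". The risk table in Section 12.1 has a row headed "Late: Any time after completion of treatment", and its one entry is interstitial lung disease, in the rare column. A window that closes on the day treatment ends has no room for such events, although the trial pays for a contact 12 weeks later at which staff ask about AEs.

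Subjects who stop early add a second difficulty. They include those withdrawn for intolerable AEs (Section 6.6), whose course after the drug is of particular interest. They attend an Early Termination Visit and receive the call, but they have no Visit 15, so neither window has a stated end for them. Sites and analysts would have to choose one.

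**Working it through.** The point rests on the text and the schedule. There is no power or alpha figure to reproduce.

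**1. Which visit is meant.** Section 8.5.3 gives a visit number (15) and a phase (Follow Up) that do not belong together under Sections 6.2.11 and 6.3. If the number is right, the phase label is wrong and the window ends with treatment. If the phase is right, the number should be 16, and recording under Section 9.2 stops before the window closes. Neither reading agrees with every section.

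**2. What each rule does with an AE.**

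| AE | Section 9.2 as written | Section 8.5.3 read as Visit 15 |
|---|---|---|
| Starts before Visit 15, first mentioned at Visit 16 | within the window by date of occurrence | counted if it started or worsened after first dose |
| Starts or worsens between Visit 15 and Visit 16 | outside | outside |
| Any AE after an Early Termination Visit | no end point stated | no end point stated |

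Both rules work by date of onset or worsening, not by date of report.

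**3. Follow-up belongs to participation.** Section 4.4 gives up to 73 weeks. With 28 days of screening, 13 months of treatment and 12 weeks of follow-up:

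4 + 13 × (365.25 / 12 / 7) + 12 = 4 + 56.5 + 12 = 72.5 weeks, which rounds to 73.

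So the plan's own figure includes the period that AE recording leaves out.

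**4. Share of time uncovered**, as follow-up / (treatment + follow-up), with a month taken as 4.35 weeks:

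- 12-month completer, call at 12 weeks: 12 / (52 + 12) = 18.8%.
- Smallest share, 13 months and a call at 10 weeks: 10 / (56.5 + 10) = 15.0%.
- Largest share, 11 months and a call at 14 weeks: 14 / (47.8 + 14) = 22.7%.

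As written, planned coverage after Visit 15 is 0 weeks. With both windows run to Visit 16 it is 10 to 14 weeks.

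**5. Number of events.** Section 12.1 gives only a band, below 5 in 100, for the late event. It gives no rate for the 12 weeks after treatment, and interstitial lung disease also appears in the on-therapy (delayed) row. No count of missed events follows from this.

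**The case against.** The strongest reply is that this is a numbering slip. The phase label in Section 8.5.3 suggests that Visit 16 was intended. Section 9.2 also calls for all AEs to be recorded, and Section 9.1.1 defines an AE by the course of the study, which includes follow-up. That may explain the error, but Section 9.2 gives Visit 15 too, and the calendar leaves eCRF entry blank at Visit 16, so correcting one number would not settle the matter.

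The second reply is that late events are not lost. Section 9.4.2 sends every SAE, and every unexpected and related AE, to the Lead Principal Investigator and states no end date. Section 9.4.3 requires IRB reporting of unexpected and related AEs during or after the study. This stands, with two limits. These are reporting channels and do not put an event into the treatment-emergent analysis. A non-serious late event that is expected or judged unrelated has no assured route, and interstitial lung disease may not qualify as unexpected because the protocol lists it.

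Three stronger readings are tempting, and the documents do not support them:

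- *Everything reported at the Visit 16 call is dropped.* The windows go by onset or worsening, so an earlier AE first mentioned there stays in.
- *The window misses the whole washout for everyone.* The half-lives in Section 1.2.2.1 (79 h, or 113 h with hepatic impairment) give 5 × 79 / 24 = 16.5 days and 5 × 113 / 24 = 23.5 days. The five-half-life rule is an outside assumption, and Section 5.2 lets improving patients stay on sirolimus, so washout does not begin at Visit 15 for all completers.
- *Early terminators are undercounted.* Section 6.7 and the calendar provide AE assessment and eCRF entry at their last visit. A missing end point leaves the cutoff undefined but does not by itself remove data.

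**Conclusion.** The point holds. Followed as written, Sections 9.2 and 8.5.3 leave AEs that start or worsen after Visit 15 out of the AE analysis, give early terminators no closing date, and disagree with the visit schedule and the calendar. The gap is 10 to 14 weeks, about 19% of the time from first dose to last contact for a 12-month completer and roughly 15% to 23% across the allowed windows. These are shares of calendar time, and they assume that Visit 15 in Section 8.5.3 means the visit so numbered elsewhere.

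This should be fixed, but it is not critical. The primary endpoint is CBR, the planned summaries are descriptive, no AE-based threshold is specified, and serious late events still reach the Lead Principal Investigator. What is at stake is the completeness of the late safety data in a trial of at most 24 evaluable subjects.

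**What to change.** - In Sections 9.2 and 8.5.3, replace Visit 15 with Visit 16 (12 ± 2 weeks after the End of Treatment or Early Termination Visit), and drop the mismatched phase label. This also gives early terminators an end point.
- In Section 15.3, mark the eCRF AE-recording row at Visit 16. In Section 6.3.1, add recording of AEs to the content of the call. Without these two edits the new wording would conflict with the schedule.
- Tabulate AEs with onset after the last study dose separately, split by whether the subject continued sirolimus off study. The call already asks this.

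The cost is wording in four places, plus entry and coding of AEs from a call that is already made. AE counts may rise slightly. The change should come before database lock, because events that were not recorded may not be recoverable. It covers the 12-week call only and would not reach the full 6 months mentioned in Section 1.2.2.1. The safety report should state that limit.
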